1. SUMMARY OF THE STUDY

Background. Laparoscopic cholecystectomy is one of the most commonly performed surgical procedures worldwide. One of its most serious complications is injury to the main bile duct, with an incidence of less than 1%. There are different surgical strategies that attempt to reduce this complication, with indocyanine green fluorescence cholangiography being one of the most recent to appear. This technique is becoming a great tool during laparoscopic cholecystectomy. Despite the boom in the procedure, there is currently a wide disparity in the protocols for administration of indocyanine green during the procedure.

Objectives. The main objective of the study is to analyse whether there are differences between different types of doses and administration intervals of indocyanine green to obtain quality fluorescein cholangiography during laparoscopic cholecystectomy. In addition, factors influencing the results of the technique will be sought.

Material and Methods. Open multicentre randomised clinical trial with 4 intervention groups (two doses and two administration times). The expected duration of the study will be 12 months. The main variables to be studied will be the degree of identification critical anatomical structures during laparoscopic cholecystectomy. Patients will be analysed per protocol, without intermediate analyses.

Symptomatic cholelithiasis is a highly relevant pathology in the world population, with prevalence rates of up to 20%. Regardless of the symptom or complication causing cholelithiasis, the current standard treatment is cholecystectomy, preferably through the minimally invasive laparoscopic approach(1,2). One of the most serious complications is injury to the main bile duct (MBV). Although the incidence of this complication is less than 1% (0.3-0.7% in different series), the consequences are very important. LVB is associated with a significant increase in patient morbidity and mortality, a significant deterioration in quality of life, a major increase in healthcare costs and significant medical-legal consequences(3). Misidentification of gallbladder anatomy has been described as one of the main factors in LVB(4). This could be favoured by the great anatomical variability of this region and the inflammatory changes that occur in many patients.

To date, there have been many recommendations to reduce the incidence of this complication, perhaps the most widely implemented being the critical safety view (CSV) published by Strasberg in 1995(5). Other techniques, such as the B-SAFE rule, are in the process of implementation(6). A recent approach using artificial intelligence and *machine learning* has been applied in the field of safe laparoscopic cholecystectomy (LC)(7). Among invasive methods, intraoperative cholangiography (IOC) has classically been the most widely used system for the prevention and early detection of LVB, as well for the diagnosis of choledocholithiasis(8). However, the disadvantages of this technique are the use of ionising radiation, the learning curve, the need prior surgical dissection and consequently the possibility of iatrogenic injury, as well as the need for infrastructure, organisation and coordination that is not widely available(9). Furthermore, it has not been shown to decrease the incidence of LVB.

Near-infrared (NIR) fluorescence cholangiography (FC) is a relatively recent technique(10) that applies the fluorescent property and biliary-only elimination of indocyanine green (IV) to map the extrahepatic biliary tree(3). VI has previously been described in the fields of cardiology, ophthalmology and currently in hepatology for the study of hepatic functional reserve(11). CF-VI allows minimally invasive, real-time visualisation of the anatomy of the extrahepatic bile duct. It is a fast method with a minimal learning curve. In addition, it does not require prior surgical dissection and costs less than CIO. However, it is currently not widely available and requires a dedicated imaging infrastructure(9,12). Recently, CF-VI has been shown to be superior to traditional white light CL in reducing LVB(13), and a 2021 meta-analysis estimates that this technique could significantly reduce LVB during CL(14). However, it has not yet been shown to be significantly superior to CIO(9,12). Furthermore, different authors show disparate rates

anatomical visualisation depending on the characteristics of the patient, the pathological process, the technique used, the instruments, etc. (3,15).

Currently, there are major differences in LV administration protocols during FC in LC. The precise dose and timing of administration are key to achieve adequate visualisation of critical vascular and biliary structures and to reduce the fluorescence emitted by the liver parenchyma, which could hinder correct anatomical visualisation(15). Regarding dosage, there are a multitude of VI administration protocols, using single doses or doses adjusted for the patient's body weight. Some authors advocate administration of the IV 24 hours before the procedure in order to avoid hepatic fluorescence(16). However, in the context of major ambulatory surgery, outpatient surgery or short-stay surgery(17), we believe that this practice is not logistically feasible at present. Other groups administer LV with a variable range of time interval(15). Recent preliminary results from the European Fluorescence Image Surgery Registry show the great disparity of preoperative LV administration protocols(18). Therefore, there is a need for protocolisation of drug administration through the results of randomised clinical studies.

The investigational medicinal product is Verdye. Verdye (*Diagnostic Green* GMBH, Aschheim-Dornach, Germany) contains the active substance VI sodium as a powder for solution for injection. This product is approved by the US Food and Drug Administration (FDA), the European Medicines Agency (EMA) and the Spanish Agency for Medicines and Medical Devices (AEMPS) as of 30/8/2017. It is a medical device for hospital use and authorised diagnostic centres. VI is a water-soluble agent with a peak spectral absorption of 800 nm. Once administered intravenously, it has an affinity for plasma proteins (β -apolipoprotein B in 95% of cases), remaining constant in the intravascular space. The IV does not undergo any metabolism process in the body. The uptake of the drug from plasma is exclusively hepatic, with biliary excretion within 30 minutes to 2 hours after intravenous injection. The fluorescent characteristics of the product appear after stimulation with near-infrared light beams (700-900 nm). It is indicated for cardiac, circulatory and microcirculatory diagnostics, liver function diagnostics and ophthalmic angiography.

Risks from the administration of the medicinal product are rare. Severe allergic reactions have been reported in one in 10,000 patients, causing symptoms such as: constriction of the throat, pruritus, blotchy skin, urticaria, coronary artery spasm, facial oedema, shortness of breath, chest tightness or pain, tachycardia, low blood pressure, dyspnoea, heart failure or cardiac arrest, restlessness, nausea, sensation of heat, flushing. The possibility of severe allergic reaction is higher in patients with severe renal insufficiency.

The route of administration of the IV will be intravenous, as specified in its data sheet. The drug administration protocols will be divided according to the dosage and time interval until surgery, as detailed below:

- **Dosage.** 2 groups: fixed bolus dose of 2.5 mg and bolus dose adjusted for body weight (0.05 mg/kg total body weight).

- **Time of administration.** On admission (>3 hours prior to surgery) and immediately preoperatively (15-30 minutes prior to surgery).

There is no treatment period as it is considered a diagnostic method. This period shall include intraoperative time.

The investigator shall ensure that this study is conducted in accordance with the principles of the 1964 Declaration of Helsinki and its subsequent revisions, GCP as well as

The study will be conducted in accordance with the ICH guidelines and in full compliance with ethical and deontological standards. Individuals participating in this study will be qualified by education, training and experience to perform their respective tasks.

The study population in this CEA is patients with an indication for elective, scheduled or early CL. The inclusion criteria are detailed below:

- Over 18 years of age.
- Autonomy, self-sufficiency and independence.
- Indication of CL programmed:
 - Symptomatic cholelithiasis: history of biliary colic, acute calculous cholecystitis, choledocholithiasis, acute ascending cholangitis of calculous origin or acute calculous pancreatitis.
 - Gallbladder polyps with indication for laparoscopic surgery.
 - Vesicular adenomyomatosis with indication for laparoscopic surgery.
- Indication for early LC (<72 hours of admission for acute calculous cholecystitis/acute calculous cholecystitis/complicated biliary colic).
- Indication of deferred emergency CL.
- Understanding information.
- Signing the informed consent form.

The exclusion criteria are detailed below:

- Under 18 years of age.
- Incapacity.
- Pregnancy or breastfeeding.
- Chronic kidney disease (Stage> IIIb).
- Adverse reactions or allergies prior to IV.
- Previous adverse reactions or allergies to VI excipients.
- Confirmed adverse reactions or allergies to iodinated contrast agents.
- Functional thyroid pathology (hyperthyroidism, thyroiditis, toxic multinodular goitre, functioning thyroid adenoma).
- Urgent non-deferrable/emergent gallbladder surgery.
- Initial surgery by laparotomy.
- Previous suspicion of gallbladder carcinoma.
- Inability to understand the information needed to participate in the study.
- Refusal of inclusion in the study protocol.

8. Aim and Purpose of the Trial

The objectives of this CE are detailed :

- **Main objective.** To analyse whether there are differences between different doses (single dose and weight-adjusted dose) and different VI administration intervals to achieve ideal visualisation of biliary structures during CF in LC.

- **Secondary objectives.**
 - 1. To analyse the influence of body mass index on FC outcomes during CL.
 - 2. To analyse the influence of the type of biliary pathology requiring surgery on the results of FC during LC.
 - 3. To analyse the influence of the type of surgery (elective/early/ delayed surgery) on the outcome of FC during LC.
 - 4. To analyse the influence of previous inflammatory changes on the results of FC during LC.
 - 5. To analyse the influence of previous gallbladder or bile duct instrumentation on the results of FC during LC.
 - 6. To analyse the influence of different laparoscopic imaging systems on the results of FC during LC.
 - 7. To analyse the rate of intraoperative complications related to CF during LC.
 - 8. To analyse the rate of postoperative complications related to CF during LC.
 - 9. To analyse the impact of FC during LC on general surgeons and/or surgeons specialised in hepatobiliopancreatic pathology and their subjective assessment of the procedure.
 - 10. To assess the impact of a history of previous liver disease on fluorescein cholangiography.

[figure not shown]
9. Trial Design

For this JU, the following key variables to be assessed in the trial are determined. Primary variables:

- Identification of biliary structures prior to dissection of the hepatocystic triangle.
 - Identification of cystic duct (yes/no).
 - Identification of common bile duct (yes/no).
 - Identification of the junction of the cystic duct with the common bile duct (yes/no).
 - Identification of the junction of the cystic duct with the gall bladder (yes/no).
 - Identification of the common hepatic duct (yes/no).
 - Identification of anatomical variables (yes/no. Specify).
- Identification of biliary structures after dissection of the hepatocystic triangle.
 - Identification of cystic duct (yes/no).
 - Identification of common bile duct (yes/no).
 - Identification of the junction of the cystic duct with the common bile duct (yes/no).
 - Identification of the junction of the cystic duct with the gall bladder (yes/no).
 - Identification of the common hepatic duct (yes/no).
 - Identification of anatomical variables (yes/no. Specify).
- Degree of identification of biliary structures prior to dissection of the hepatocystic triangle (1=poor, 2=sufficient, 3=sufficient, 4=good, 5=excellent).

- Degree of identification of biliary structures after dissection of the hepatocystic triangle (1=poor, 2=sufficient, 3=sufficient, 4=good, 5=excellent).
- Degree to which fluorescence cholangiography was perceived as useful for surgery (0=not useful, 1=moderately useful, 2=very useful).
- Degree to which the fluorescence of the liver background (contrast between liver and ducts) was perceived as disturbed (0=absence of disturbance, 1=slightly disturbed, 2=disturbed visualisation, but cystic-choledochal junction was clearly visible before dissection, 3=disturbed visualisation and cystic-choledochal junction was only visible after dissection, 4=very disturbed: it was impossible to visualise the biliary structures correctly).

The design of this CE is reflected in the following flowchart.

G1: Grupo 1, G2: Grupo 2, G3: Grupo 3, G4: Grupo 4, VI: Verde de indocianina

10. Research Product Characteristics (RPP)

Verdye 25 mg contains VI sodium powder for solution for injection. VI is a water-soluble agent with a peak spectral absorption of 800 nm. It is approved for diagnostic use only and is indicated for the measurement of the excretory function of the liver.

liver. This medicine is included in the University Hospital of Salamanca and routinely used in the General and Digestive System Surgery Service.

Diagnostic use of this medicinal product should be performed under surveillance. The total daily dose should be less than 5 mg/kg body weight. The medicinal product should not be diluted with saline solutions and be stored at a temperature below 30°C. Administration should be intravenous and handled under sterile conditions. A previous tolerance test with Verdyne in which no problems have been encountered should not be considered an absolute guarantee of safety. Patients with end-stage renal failure have a higher rate of adverse effects. Two cases of death from anaphylactic reaction following administration of IV during cardiac catheterisation have been reported.

The delivery of the IMP will be carried out through the Hospital Pharmacy Service. Each vial of medicine will be for individual use, discarding the remaining active ingredient according to the protocol for handling pharmacological products. A document will be sent to the Hospital Pharmacy Service detailing the vials needed for the study in each centre (estimating 10 additional vials per centre). These vials will be stored in the operating room storerooms in a place outside the usual product use and with a "only use for DOTIG study" label. Once the study is completed, unused VI vials will be returned to the Hospital Pharmacy Service. A drug traceability document will be signed to ensure proper delivery and storage of the drugs.

VI administration protocols will be prespecified depending on the randomised treatment group. The product will be prescribed by the medical staff once the dosage and administration interval is known.

11. Selection and Withdrawal of Subjects

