11.1. Criteria for inclusion of subjects

- Over 18 years of age.
- Autonomy, self-sufficiency and independence.
- Indication of CL programmed:
 - Symptomatic cholelithiasis: history of biliary colic, acute calculous cholecystitis, choledocholithiasis, acute ascending cholangitis of calculous origin or acute calculous pancreatitis.
 - Gallbladder polyps with indication for laparoscopic surgery.
 - Vesicular adenomyomatosis with indication for laparoscopic surgery.
- Indication for early LC (<72 hours of admission for acute calculous cholecystitis/acute calculous cholecystitis/complicated biliary colic).
- Indication of deferred emergency CL.
- Understanding information.
- Signing the informed consent form.

11.2. Exclusion criteria for subjects.

- Under 18 years of age.
- Incapacity.
- Pregnancy or breastfeeding.

- Chronic kidney disease (Stage> IIIb).
- Adverse reactions or allergies prior to IV.
- Previous adverse reactions or allergies to VI excipients.
- Confirmed adverse reactions or allergies to iodinated contrast agents.
- Functional thyroid pathology (hyperthyroidism, thyroiditis, toxic multinodular goitre, functioning thyroid adenoma).
- Urgent non-deferrable/emergent gallbladder surgery.
- Initial surgery by laparotomy.
- Previous suspicion of gallbladder carcinoma.
- Inability to understand the information needed to participate in the study.
- Refusal of inclusion in the study protocol.

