 - Indication for surgery [Symptomatic cholelithiasis (biliary colic, acute cholecystitis, choledocholithiasis, acute ascending cholangitis, acute lithiasic pancreatitis), gallbladder polyps, gallbladder adenomyomatosis].
- **Perioperative period:**
 - Date of entry (dd-mm-yyyy).
 - Time of entry (hour:minutes)
 - Date of surgery (dd-mm-yyyy).
 - Time of surgery (hour:minutes).

- Type of surgery (elective/early/ delayed emergency).
 - Grade of cholecystitis in case of early surgery / delayed emergency (18th Tokyo Classification).
 - Intervention group (group 1/group 2/group 3/group 4).
 - Characteristics of the procedure. IV dosage (fixed dose/weight-adjusted dose). IV administration interval (>3 hours preoperatively, 15-30 minutes preoperatively). Immediate adverse reactions (yes/no. Specify). Number of trocars (3/4). Imaging system used (Olympus/Karl-Storz/Stryker). Optics used (0º/30º). Gall bladder puncture/emptying (yes/no). Bile culture (yes/no). Result of bile culture if any (specify).
 - Conversion to laparotomy (yes/no), intraoperative complications (yes/no), specification of intraoperative complications (cystic artery injury, right hepatic artery injury, liver injury with/without bleeding, gallbladder opening (intrapertitoneal biliary contamination: yes/no, lithiasis outflow into peritoneal cavity: yes/no), hollow viscus perforation, trocar bleeding, other). Operating time (minutes).
- **Postoperative period:**
 - Hospital stay (days), postoperative complications (intra-abdominal haematoma, bilioma, abscess, paralytic ileus, surgical site infection-ISQ, trocar evisceration, trocar eventration, others), postoperative complications according to Clavien-Dindo classification, bile duct injury (Strasberg classification), time of diagnosis bile duct injury (intraoperative / postoperative), treatment of bile duct injury (immediate surgical, radiological, endoscopic or delayed surgical). Mortality during admission (yes/no), 30-day mortality (yes/no), causes of mortality (specify). Adverse drug reactions within 30 days (yes/no. Specify).

All preoperative data will be collected for patients withdrawn from the study, as well the type of complication developed and any adverse events during the first 30 days of the study (if any). Subjects will not be replaced in the study. The follow-up period will be identical for subjects who do not undergo the study intervention.

15. Monitoring

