Required data to be accurately recorded in CRDs and agree with source data. Revised according to the Monitoring Manual.

- Patient identification.
- Date and time of surgery.
- Dose and time of VI administration.
- Target variables (set out above).

After each monitoring, the monitor will be able to generate a discrepancy document with the inconsistencies and errors detected in the study. These problems can be communicated through the CDRe or by e-mail.

16. Researcher and collaborators

The principal investigator shall maintain a register of all persons involved in the trial (medical, nursing, and other personnel). He/she shall confirm that appropriate training relevant to the trial is given to all such personnel and that any new information relevant to the conduct of the trial is conveyed to the personnel involved.

17. Facilities

- **Hospitalisation ward.** This is where the patient is admitted prior to surgery. This is where all mandatory documentation is checked and the patient is prepared for surgery.
- **Pre-operative conditioning room.** A surgical checklist and a new preparation of the patient will be performed.
- **Operating theatres.** In addition to the equipment necessary for any laparoscopic surgical activity, which is no different from the study activity, these operating theatres will be equipped with the necessary equipment to perform CF-VI (optics, light cable and compatible image processing system).
- **Postoperative recovery room.** Controlled by the Anaesthesiology and Resuscitation Service.
- **Outpatient clinics.** Place where the postoperative control will be carried out after the patient is discharged.
- **Hospital Pharmacy Service.** Responsible for dispensing the medicine.
- **Operating theatre storeroom.** This is where the necessary equipment and drugs are stored, including the active ingredient of the study.

[figure not shown]
18. Treatment of Subjects

Subjects included in this CE will be treated with VI [Verdye (Diagnostic Green GMBH, Aschheim-Dornach, Germany)]. The following patient groups are established in the CE.

- **Group 1.** Fixed dose 2.5 mg with IV administration more than 3 hours before surgery.
- **Group 2.** Fixed dose 2.5 mg with immediate pre-operative VI administration (15-30 minutes before surgery).
- **Group 3.** Weight-adjusted dose (0.05 mg/kg total body weight) with administration of the LV more than 3 hours before surgery.

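### The early-administration arms have a 3-hour floor but no ceiling, so the timing result averages over intervals that probably follow urgency, and the SAP never uses the actual interval

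*Protocol*

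**What the plan says.** Section 7 of the protocol defines the timing factor as "On admission (>3 hours prior to surgery) and immediately preoperatively (15-30 minutes prior to surgery". Section 18, which defines the four groups, drops the reference to admission: Group 1 is "Fixed dose 2.5 mg with IV administration more than 3 hours before surgery", and Group 3 has the same interval with the weight-adjusted dose. Section 1 of the SAP also gives only the 3-hour floor. None of these places gives a maximum.

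Eligible patients include those with "Indication for early LC (<72 hours of admission for acute calculous cholecystitis/acute calculous cholecystitis/complicated biliary colic" and those with "Indication of deferred emergency CL" (Sections 7 and 11.1). The second group has no admission-to-surgery window.

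On data, Section 14 lists the interval as a two-category item: "IV administration interval (>3 hours preoperatively, 15-30 minutes preoperatively". The same section collects clock times of entry and of surgery, and Section 15 names the time of indocyanine green administration among the data that must be accurately recorded and agree with source.

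On analysis, Section 2 of the SAP compares the labels G1 to G4. Type of surgery appears in the baseline comparison (SAP Section 1) and as a secondary predictor (SAP Section 3c). No analysis uses actual hours, and none crosses timing with type of surgery. Section 1 of the protocol says the analysis is per protocol.

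**The concern.** The main objective asks whether the administration interval matters. An elective patient injected on the day of surgery and an inpatient injected on admission and operated on days later carry the same label in G1 or G3. If outcome changes with hours since injection, the early-level result is an average over whatever mix of intervals the centres happened to produce, and a reader elsewhere would not know which interval it describes.

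The protocol gives some reason to expect a change. Section 7 calls precise timing key, and reports that some authors dose 24 hours ahead to avoid liver fluorescence. Disturbance from the liver background is one of the trial's primary variables.

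Secondary objective 3, the influence of type of surgery, is also exposed. If long intervals in G1 and G3 occur mainly in acute patients, those arms cannot show whether a difference comes from the acute setting or from time since injection.

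**Working it through.** The plan gives no figure for the interval or its distribution, so there is no stated number to reproduce. The check compares the definitions and works out what they permit.

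1. **Range permitted.** Floor for G1 and G3: 3 h (Sections 7 and 18). Limit for early surgery: under 72 h from admission (Section 11.1). With injection at admission, the interval runs from 3 h to almost 72 h: a span of 72 − 3 = 69 h and a ratio of 72 / 3 = 24. For G2 and G4 the span is 30 − 15 = 15 min. For deferred emergency surgery the documents set no ceiling, so 72 h is not its limit.

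2. **Two rules for one arm.** A patient injected later in the admission, but still more than 3 h before surgery, meets Section 18 and not the literal wording of Section 7. A patient operated on within 3 h of admission cannot meet both parts of Section 7. Which rule applies decides who is in the per-protocol set.

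3. **Is the randomised contrast confounded by type of surgery?** Section 18 specifies 1:1:1:1 unstratified block randomisation, so type of surgery is balanced between timing levels in expectation. The chance imbalance, with about 100 patients per level (200 / 2) and an assumed non-elective share q, has standard error √(2q(1−q)/100), approximating by simple randomisation:
 - q = 10%: SE 0.042; probability of a difference over 10 points 1.8%
 - q = 20%: SE 0.057; 7.7%
 - q = 30%: SE 0.065; 12.3%
 - q = 40%: SE 0.069; 14.9%

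 A large imbalance is unlikely, and adjustment would deal with it.

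4. **Inside G1 and G3.** Randomisation does not assign the interval within these arms. If injection follows admission, hours since injection equal hours from admission to surgery, which depend on urgency. The SAP has no step that separates the two.

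5. **How many patients?** The documents do not say. With about 50 per arm (200 / 4) and an assumed q of 10%, 20%, 30% or 40%, there would be 5, 10, 15 or 20 non-elective patients in each of G1 and G3. These are upper counts, since not all would have a long interval. If their intervals were spread evenly over 3 to 72 h (a further assumption), the share of an early arm beyond 24 h would be q × (72 − 24)/69: about 7%, 14%, 21% and 28%.

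6. **Can the interval be recovered?** Interval = time of surgery (Section 14) minus time of administration (Section 15). Both are required data, although the item list in Section 14 shows only the category for administration.

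**The case against.** The strongest reply is that more than 3 hours against 15-30 minutes is a legitimate pragmatic contrast, randomised and usable in practice. That stands: the early level is open-ended, but it is not undefined.

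A reader might infer several stronger things that the documents do not support:

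- **That timing is confounded with type of surgery in the main comparison.** It is not; step 3 shows why.
- **That the stated pharmacology proves 3 h and 72 h differ.** Section 7 describes the dye "with biliary excretion within 30 minutes to 2 hours after intravenous injection". Both intervals lie beyond that window, so this figure does not separate them.
- **That the protocol contradicts itself on 24-hour dosing.** Section 7 does say "we believe that this practice is not logistically feasible at present", but only for ambulatory, outpatient or short-stay surgery. Acute inpatients are a different setting.
- **That intervals near 72 h will be common.** This is a ceiling for early surgery only. It needs Section 7 to be taken literally and injection at the moment of admission, whereas consent and allocation must come first.
- **That the interval cannot be recovered.** Section 15 already requires the time of administration.

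It is also fair to say that Section 1 of the SAP describes most patients in one centre as elective, in the past tense. The affected group may be small, and changing the arm definition may come too late. Non-elective subgroup estimates would be weak across 16 primary variables (12 yes/no items and 4 scales). None of this explains why actual hours are left out of the analysis.

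**Conclusion.** The concern holds in a limited form. The early level has no upper limit, its link to admission is stated in one section and omitted from the group definitions, and eligibility allows intervals from 3 h to almost 72 h in early surgery, with no stated ceiling in deferred emergency surgery. The randomised timing comparison remains valid as a comparison of assigned strategies, but it averages over an interval that the SAP neither describes nor uses. Within G1 and G3, secondary objective 3 cannot separate type of surgery from time since injection.

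The size in patients is unknown. The counts above rest on assumed non-elective shares of 10-40%, and the proportions beyond 24 h rest also on an assumed even spread. That interval follows urgency is an inference from the admission rule, not a reported fact. If nearly all patients are elective with same-day injection, the practical effect will be small, and reporting the interval would show it. This is a worthwhile, inexpensive improvement and not a fatal flaw.

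**What to change.** **Protocol.** Reconcile Sections 7 and 18 on whether admission or the 3-hour floor defines the early arms, and state which rule determines membership of the per-protocol set. Whether to set a range, and which, is for the sponsor.

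**CRDe.** Hold the clock date and time of injection alongside the existing category.

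**SAP.** Add four items:

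- Report the actual interval (median, quartiles, range) by arm and type of surgery.
- Give the timing contrast (G1 and G3 against G2 and G4) adjusted for type of surgery, and also within elective and within early or deferred surgery.
- Word the timing conclusion in terms of the intervals observed.
- If outcome is analysed against hours since injection within G1 and G3, adjust for type of surgery and label the analysis exploratory and non-randomised.

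**Cost.** One date-time field that Section 15 already calls for, one clarification, and a few SAP lines. If recruitment is already complete, the SAP items should still be possible from recorded times. The price is a narrower timing conclusion and imprecise estimates in non-elective patients.
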